## **Phase II**

Twenty four patients (not including any patients from the phase I portion of the study) will receive cycles of therapy according to the following starting schedule:

RUXOLITINIB at dose defined by Phase I portion of the study, on days 1-28 of each cycle

Decitabine 20 mg/m^2 IV daily for 5 days

Cycles will be repeated every 4 to 6 weeks depending on tolerance and the recovery of counts.

RUXOLITINIB will be provided by the sponsor (Incyte) free of charge to the participating patients for a maximum period of up to 24 months. Any used or expired study drug will be disposed of accordance to the MD Anderson policy.

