#### **Phase 2 study**

We will accrue a maximum of 24 patients at a rate of 2 patient per month. The primary outcome for this trial is overall response rate.

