## Phase II

Phase II part is a single arm study using the dosage level recommended from phase I. The patients treated at the MTD in phase I will not be included in phase II part, and the sample size for phase II is a maximum of 24 patients. The trial will be continuously monitored for efficacy and toxicity (non-hematological  $\geq$ grade 3 and hematological  $\geq$ grade 4). The method of Thall, Simon, and Estey will be used to perform interim efficacy and safety monitoring.

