### **Efficacy and Toxicity Monitoring**

The primary endpoint is the overall response (CR+CRi) after three cycles of treatment. Overall response (OR) and toxicity will be monitored simultaneously using the Bayesian approach of Thall, Simon, Estey (1995, 1996) and the extension by Thall and Sung (1998. The historical data suggested the overall response rate is 10% and the target overall response rate with the experimental treatment is 30%. This regimen of the combination treatment will be considered worthy of further investigation if it elicits an increase in OR to 20% with acceptable toxicity. A  $>20\%$  toxicity rate is considered unacceptable. Thus, interim monitoring rules, assuming the prior distributions above, were constructed that meet the following two conditions,

$$\Pr(0.2 < \theta_{E, \text{Toxicity}} | \text{data}) > 0.80 \text{ and}$$

$$\Pr(\theta_{E, \text{OR}} > 0.3 | \text{data}) < 0.025.$$

where  $\theta_{E, \text{Toxicity}}$  and  $\theta_{E, \text{OR}}$  are the true toxicity and overall response for the combination treatment, respectively. The first rule provides for stopping the study if excessive toxicity is highly probable (i.e., probability  $>80.0\%$ ) for the combination treatment. The second condition will stop the study early if the data suggest that it is unlikely (i.e., probability  $< 2.5\%$ ) that OR rate of the combination treatment is 30%. Monitoring for toxicity and futility will not begin until 4 patients have been evaluated, and cohort size for future evaluations is 2.

The monitoring rule for the toxicity rate, based on these assumptions and monitoring conditions above is found in Table 7. For example, accrual will cease if 3 or more patients experience toxicities among the first 6 patients.

Table 7. Stop accrual if the number of toxicities is greater than or equal to indicated (i.e., # patients with toxicities) among the number of patients evaluated							
# patients evaluated	2-4	6-8	10-12	14-16	18-20	22	24
# patients with toxicities	2-4	3-8	4-12	5-16	6-20	7-22	Always stop with this many patients

Monitoring the OR rate, based on the above assumptions and monitoring conditions is found in Table 8. For example, accrual will cease if 0 or fewer patients experience a response in the first 8 patients treated.

Table 8. Stop accrual if the number with OR is less than or equal to indicated (i.e., # patients with OR) among the number of patients evaluated					
# patients evaluated	2-6	8-12	14-18	20-22	24

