# patients with OR	Never stop with this many patients	0	0-1	0-2	Always stop with this many patients

Multc Lean Desktop (version 2.1.0) was used to generate the toxicity and futility stopping boundaries and the OC table (Table 9). In order to utilize the software for the design, a 30% response rate and beta (0.6, 1.4) priors were assumed for the standard treatment response distribution and experimental treatment response prior distribution, respectively. In addition, a 30% toxicity constant rate and beta (0.6, 1.4) priors were assumed for the standard treatment toxicity constant rate and experimental treatment toxicity prior distribution, respectively.

The probability of stopping the study early if the true response rate of the combination treatment was not better than 30% and the true toxicity rate is 20% was 44%. Probabilities of stopping early for high true toxicity rates (i.e., 40%) were 10% when the true OR rate was 10% and 39% when true OR rate was 20%.

Table 9. Operating characteristics for simultaneous monitoring response and toxicity rates for patients treated with combination treatment

True OR	True Toxicity Rate	True Probability Vector (OR/Tox, OR/NoTox, NoOR/Tox, NoOR/NoTox)	Probability of Stopping	Average number of patients treated
10%	10%	(0.01, 0.09, 0.09, 0.81)	0.7689	14
10%	20%	(0.02, 0.08, 0.18, 0.72)	0.8437	12
10%	30%	(0.03, 0.07, 0.27, 0.63)	0.9325	9
10%	40%	(0.04, 0.06, 0.36, 0.54)	0.9827	7
20%	10%	(0.02, 0.18, 0.08, 0.72)	0.3679	19
20%	20%	(0.04, 0.16, 0.16, 0.64)	0.5724	15
20%	30%	(0.06, 0.14, 0.24, 0.56)	0.8153	11
20%	40%	(0.08, 0.12, 0.32, 0.48)	0.9526	7
30%	10%	(0.03, 0.27, 0.07, 0.63)	0.1676	21
30%	20%	(0.06, 0.24, 0.14, 0.56)	0.4369	17
30%	30%	(0.09, 0.21, 0.21, 0.49)	0.7568	12
30%	40%	(0.12, 0.18, 0.28, 0.42)	0.9379	8
40%	10%	(0.04, 0.36, 0.06, 0.54)	0.1036	22
40%	20%	(0.08, 0.32, 0.12, 0.48)	0.3936	18
40%	30%	(0.12, 0.28, 0.18, 0.42)	0.7381	12
40%	40%	(0.16, 0.24, 0.24, 0.36)	0.9328	8

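### Table 9 assumes every outcome is known at enrolment; with a 12–18 week response lag and 2 patients per month, its low-response rows overstate how early accrual would be halted

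*Combined protocol and SAP*

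**What the plan says.** Section 13.0 (Efficacy and Toxicity Monitoring) sets the endpoint: "The primary endpoint is the overall response (CR+CRi) after three cycles of treatment". Section 8.1 (Phase II) gives the cycle length: "Cycles will be repeated every 4 to 6 weeks depending on tolerance and the recovery of counts". The Phase 2 study paragraph in Section 8 gives the pace: "We will accrue a maximum of 24 patients at a rate of 2 patient per month".

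The look schedule is: "Monitoring for toxicity and futility will not begin until 4 patients have been evaluated, and cohort size for future evaluations is 2". Tables 7 and 8 are instructions to stop accrual, indexed by patients evaluated. The worked examples are that "accrual will cease if 3 or more patients experience toxicities among the first 6 patients" and that "accrual will cease if 0 or fewer patients experience a response in the first 8 patients treated"; the second counts patients treated rather than evaluated.

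Table 9, titled "Operating characteristics for simultaneous monitoring response and toxicity rates for patients treated with combination treatment", then reports a probability of stopping and an average number of patients treated for 16 combinations of true response (OR) and toxicity rates. The accompanying text gives priors and rates, but no accrual rate, evaluation delay or pause rule. Staggered enrolment is described only for the phase I cohorts.

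**The concern.** The action attached to both boundaries is to stop accrual. A look that needs three-cycle responses on 8 patients happens only when the eighth has had time to complete three cycles, and recruitment has continued meanwhile. If Table 9 ignores that interval, its average number treated is too low, and its stopping probability cannot be read as the chance of halting accrual before it is complete.

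This matters most at a true response rate of 10%, which the plan takes as the historical rate. That is the no-benefit case the futility rule exists for, and anyone judging patient protection from Table 9 would see a larger saving than the stated timing delivers.

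**Working it through.** **Inputs from the plan.** Response after three cycles; cycles of 4–6 weeks; 2 patients per month; maximum 24; first look at 4, then every 2; beta(0.6, 1.4) prior for both experimental rates; stopping criteria Pr(toxicity > 0.2) > 0.80 and Pr(OR > 0.3) < 0.025; response and toxicity independent, as in Table 9's probability vectors.

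**Step 1: boundaries.** With x events in n patients the posterior is Beta(0.6 + x, 1.4 + n − x). Applying the two criteria gives:
- Toxicity: stop at 2 or more (n = 2–4), 3 (6–8), 4 (10–12), 5 (14–16), 6 (18–20), 7 (22).
- Futility: stop at 0 responses (n = 8–12), 1 or fewer (14–18), 2 or fewer (20–22).

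These agree with Tables 7 and 8.

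**Step 2: Table 9 with immediate outcomes.** Exact enumeration matches 15 of the 16 stopping probabilities to four decimals; the other (OR 30%/toxicity 40%) is 0.9376 against 0.9379. All average numbers agree within one patient. At OR 10%/toxicity 10% the result is 0.7689 and 13.9; the table has 0.7689 and 14. No allowance for delay is needed to obtain Table 9.

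**Step 3: entries while a response is pending.** At 4.348 weeks per month:
- 12 weeks: 12/4.348 = 2.76 months; × 2 = 5.5 patients.
- 18 weeks: 18/4.348 = 4.14 months; × 2 = 8.3 patients.

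With even spacing, patient i enters at (i − 1)/2 months, so patient 24 enters at 11.5. The futility look at n occurs at (n − 1)/2 plus the lag.
- n = 8: 3.5 + 2.76 = 6.26 months (13 enrolled), or 3.5 + 4.14 = 7.64 months (16 enrolled).
- 12-week lag, n = 20: 9.5 + 2.76 = 12.26 > 11.5, so all 24 are in. At n = 18: 8.5 + 2.76 = 11.26, so one patient is still to come.
- 18-week lag, n = 16: 7.5 + 4.14 = 11.64 > 11.5, so all 24 are in. At n = 14: 6.5 + 4.14 = 10.64, with 22 enrolled.

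**Step 4: re-simulation with the lag.** Same boundaries, no pause, response lag 12 or 18 weeks, accrual evenly spaced or Poisson. The toxicity lag of 0 or 28 days is an assumption.

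| OR / toxicity | Table 9: P(stop), mean N | P(accrual halted before 24) | Mean N |
|---|---|---|---|
| 10% / 10% | 0.7689, 14 | 0.66–0.68; about 0.60 with Poisson and 18 weeks | 17.2–19.2 |
| 10% / 20% | 0.8437, 12 | 0.73–0.78 | 14.2–16.2 |
| 20% / 10% | 0.3679, 19 | 0.29–0.33 | 20.4–21.3 |
| 30% / 20% | 0.4369, 17 | 0.42–0.43 | 17.4–18.3 |
| 30% / 10% | 0.1676, 21 | 0.15–0.16 | 21.8–22.2 |
| 40% / 10% | 0.1036, 22 | about 0.10 | 22.3–22.6 |

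The low ends in the second and third rows (0.73 and 0.29) also come from Poisson accrual with the 18-week lag. In every row the probability of ever crossing a boundary stays at Table 9's value within simulation error.

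At OR 10%/toxicity 10%, patients spared fall from 24 − 14 = 10 to between 24 − 19 = 5 and 24 − 17 = 7.

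**The case against.** **Table 9 is computed correctly.** True. There is no arithmetic error here. What is missing is a statement that outcomes are taken as immediate, and the plan's timing contradicts that assumption.

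**The stopping probability does not depend on delay.** True for eventually crossing a boundary, and the boundaries remain valid. But a crossing after patient 24 has entered halts no accrual, and the average number treated changes in any case.

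**Some failures are known early.** Section 12.0 takes patients off study at progression, Section 2.0 cites a median survival of 2.7 months for myelofibrosis in blast phase, and Section 3.2 lets cycles start early. Letting non-responders fail early with that median gives, at OR 10%/toxicity 10%, 0.69 and 16.9 patients (12-week lag, 4-week toxicity window) or 0.64 and 18.6 (18-week lag, 6-week toxicity window, Poisson accrual). The effect shrinks slightly but remains.

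**Accrual might pause at looks.** Table 9 would then stand. No phase II pause is stated, however, and it would be hard to square with 2 per month: if the trial runs to 24, eight futility looks of 12 weeks add 8 × 2.76 = 22 months, and ten looks of 18 weeks add 10 × 4.14 = 41 months.

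**Two stronger readings are not supported.** A reader might infer that the late looks can halt nothing. That is true only of the Table 8 futility boundary under even accrual; the toxicity rule in Table 7 applies at the same looks and can still halt accrual if toxicity is known early. A reader might also infer that all of Table 9 is materially too favourable. At OR 30% or more with toxicity of 10–20% and a short toxicity window, the change is about one patient or less, and a lower chance of halting a promising regimen is no harm.

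**Conclusion.** The point holds for the low-response rows, as an unstated assumption about operating characteristics. Under the plan's own accrual rate and endpoint timing, the averages there are too low by about 1.5 to 5 patients, and the stopping probabilities overstate the chance of halting accrual before patient 24. The case is clearest at the historical response rate of 10%. At OR 20% the plan itself calls the regimen worth pursuing, so a lower chance of halting is not plainly a loss, although the stated average is still too low.

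The size rests on a 12–18 week response lag, no accrual pause, and an assumed toxicity lag of 0–28 days. The last assumption drives the high-toxicity rows. If toxicity too were judged only at 18 weeks, OR 30%/toxicity 30% would go from 0.757 and 12 patients to 0.65 and 17.7. The plan defines no phase II toxicity window, so that range cannot be narrowed from the documents.

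**What to change.** Keep the boundaries in Tables 7 and 8. In Section 13.0:

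- State that accrual continues while responses are pending, and state the toxicity window used for phase II monitoring.
- Restate Table 9 with the average number treated and the probability that accrual is halted before patient 24, under 2 patients per month, a 12–18 week response lag and the stated toxicity window. Label the existing probabilities as the chance of ever crossing a boundary.
- Note which Table 8 looks can still halt accrual: with even accrual, those up to 18 patients evaluated at a 12-week lag and up to 14 at an 18-week lag.
- If accrual is instead meant to pause at looks, say so and reconcile that with the 2-per-month rate.

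The cost is one re-simulation, a revised table and less favourable stated averages.

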### Analysis method

Data analysis will be performed using SAS or S-plus, as appropriate. All patients who received at least 1 dose of the combined agents will be included in the intent-to-treat analysis for efficacy. Demographic and disease characteristics of the patients at registration will be summarized using descriptive statistics such as mean, standard deviation (SD), median and range. Overall response rates will be presented with 95% confidence intervals.

The association between response and patient and disease characteristics will be examined by two-sample t-test (or Wilcoxon rank-sum test) or Chi-square test.

The data from all patients who received the combined therapy during the study will be included for safety analysis. Safety data will include laboratory, physical exam, and adverse event reports on study patients. These descriptive summaries will be provided for all patients for each safety parameter by cycle, grade, and relationship to treatment.

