## 9.0 EVALUATION DURING TREATMENT/INTERVENTION

### Response assessment

Response assessment (RA) can be performed at the end of any cycle after cycle 1. Specific events that will prompt response assessment include of resolution of splenomegaly on exam and clearance of blasts from the peripheral blood, which will prompt bone marrow aspirate and biopsy. Patients continuing to maintain at least SD by the response criteria shown below should continue to receive ruxolitinib and decitabine until progression of disease, unacceptable toxicity or patient withdrawal. Patients may receive up to 24 cycles in this study. Patients may proceed to allogeneic stem cell transplant at any time after Cycle 1. Dose modification of ruxolitinib will be allowed after Cycle 1. RUXOLITINIB will be provided by the sponsor for a maximum of up to 2 years, after which it will be required to procure it from commercial sources.

Adverse events will be captured as long as patients are on study and will be used to fully characterize the tolerability and toxicity of this combination therapy. These events will be defined based on the NCI CTCAE version 4. Patients who withdraw from the study for any reason will be followed and seen 28 days (+/- 5 days) for an end of study visit to capture all adverse events.

Adverse events will only be captured after the first dose of RUXOLITINIB has been administered.

**Table 3** - Schedule of study procedures

Evaluation	Baseline screening	Cycle 1	Cycle 2 and beyond	Response assessment	End of Study
		At least once weekly (+/- 3 days)	At least once every 2 weeks (+/- 3 days)		(+/- 5 days)
History	x				
physical exam	x	x	x		x
Vital signs	x	x	x		x
Concomitant medications 	x	x	x		x
Adverse event assessment		x	x		x
HIV, HBV, HCV serology	x				
MUGA or Echo	x				
ECG	x				x
CT/MRI abd/pelvis without contrast,	x			x 	

if clinically indicated					
Pregnancy test	X				
CBC with differential	X	X	X		X
Chemistry 	X	X	X		X
Bone marrow biopsy	X			X 	X
Bone marrow aspirate	X			X 	X
Jak2/MPL allele burden 	X				
Correlative studies 	X				X
Chest X-ray	X				

1. Preferentially performed on the marrow, but will be performed on the peripheral blood if a specimen cannot be obtained. Allele burden will not be repeated if neither Jak2 nor MPL is mutated. The sample will be obtained in 5 ml EDTA tube.

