## **14.0 PROTECTION OF HUMAN SUBJECTS**

### **14.1 Serious Adverse Event (SAE) Reporting**

An adverse event or suspected adverse reaction is considered “serious” if, in the view of either the investigator or the sponsor, it results in any of the following outcomes:

- Death
- A life-threatening adverse drug experience – any adverse experience that places the patient, in the view of the initial reporter, at immediate risk of death from the adverse experience as it occurred. It does not include an adverse experience that, had it occurred in a more severe form, might have caused death.
- Inpatient hospitalization or prolongation of existing hospitalization
- A persistent or significant incapacity or substantial disruption of the ability to conduct normal life functions.
- A congenital anomaly/birth defect.

Important medical events that may not result in death, be life-threatening, or require hospitalization may be considered a serious adverse drug experience when, based upon appropriate medical judgment, they may jeopardize the patient or subject and may require medical or surgical intervention to prevent one of the outcomes listed in this definition. Examples of such medical events include allergic bronchospasm requiring intensive treatment in an emergency room or at home, blood dyscrasias or convulsions that do not result in inpatient hospitalization, or the development of drug dependency or drug abuse (21 CFR 312.32).

- Important medical events as defined above, may also be considered serious adverse events. Any important medical event can and should be reported as an SAE if deemed appropriate by the Principal Investigator or the IND Sponsor, IND Office.
- All events occurring during the conduct of a protocol and meeting the definition of a SAE must be reported to the IRB in accordance with the timeframes and procedures outlined in “The University of Texas M. D. Anderson Cancer Center Institutional Review Board Policy for Investigators on Reporting Unanticipated Adverse Events for Drugs and Devices”. Unless stated otherwise in the protocol, all SAEs, expected or unexpected, must be reported to the IND Office, regardless of attribution (within 5 working days of knowledge of the event).
- All life-threatening or fatal events, that are unexpected, and related to the study drug, must have a written report submitted within 24 hours (next working day) of knowledge of the event to the Safety Project Manager in the IND Office.

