- Unless otherwise noted, the electronic SAE application (eSAE) will be Utilized for safety reporting to the IND Office and MDACC IRB.

- Serious adverse events will be captured from the time of the first protocol-specific intervention, until 30 days after the last dose of drug, unless the participant withdraws consent. Serious adverse events must be followed until clinical recovery is complete and laboratory tests have returned to baseline, progression of the event has stabilized, or there has been acceptable resolution of the event.
- Additionally, any serious adverse events that occur after the 30 day time period that are related to the study treatment must be reported to the IND office. This may include the development of a secondary malignancy.

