**Investigator Communication with Supporting Companies:**

Serious adverse events (SAE) will be captured from the time of the first protocol-specific intervention, until 30 days after the last dose of drug. The investigator will inform Incyte of any SAE or pregnancy within 24 hours of being aware of the event via email and/or fax. Respective companies will be informed based on the attribution of a given event:

1. Due to RUXOLITINIB alone – These SAEs will only be reported to INCYTE.
2. Due to both the RUXOLITINIB and decitabine – These SAEs will be reported to INCYTE
3. All pregnancies will be reported to INCYTE If the investigator can't associate causality with one or the other alone then causality needs to be associated with the combination of the products. These SAEs will go to INCYTE.

Adverse events will be documented in the Leukemia-specific AE Recording and Reporting Guidelines attached in Appendix E. medical record and entered into the case report form. PDMS/ CORE will be used as the electronic case report form for this protocol. All adverse events will be captured in CRF during Phase I portion of the study. In Phase II, only Grade 3 and higher related will be captured in the CRF. Investigator or physician designee is responsible for verifying and providing source documentation for all adverse events and assigning the attribution for each event for all subjects enrolled on the trial. SAEs must be documented using the MDACC IND eSAE electronic form. This form must be completed and supplied to Incyte within 24-hours/1-business day at the latest on the following working day. The initial report must be as complete as possible, including details of the current illness and (serious) adverse event, and an assessment of the causal relationship between the event and the investigational product(s). Information not available at the time of the initial report (e.g., an end date for the adverse event or laboratory values received after the report) must be documented on a follow-up MDACC IND eSAE reporting form.

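### The all-patient safety summaries by grade and relationship do not allow for the narrower adverse event capture in the phase II CRF

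*Combined protocol and SAP*

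**What the plan says.** Section 13.0, Analysis method, includes all patients given the combined therapy in the safety analysis. It names the sources ("Safety data will include laboratory, physical exam, and adverse event reports on study patients") and then the output: "These descriptive summaries will be provided for all patients for each safety parameter by cycle, grade, and relationship to treatment". It gives no split by phase and no rule for denominators.

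Section 14.1, under Investigator Communication with Supporting Companies, sets the capture rules. For phase I: "All adverse events will be captured in CRF during Phase I portion of the study". For phase II: "In Phase II, only Grade 3 and higher related will be captured in the CRF". The same paragraph keeps the investigator responsible for "verifying and providing source documentation for all adverse events and assigning the attribution for each event for all subjects enrolled on the trial", so the medical record is meant to be complete in both phases.

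SAEs follow a separate route that does not depend on phase. Section 14.1 says that "all SAEs, expected or unexpected, must be reported to the IND Office, regardless of attribution", and that "the electronic SAE application (eSAE) will be Utilized for safety reporting to the IND Office and MDACC IRB".

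Section 9.0 states the purpose of adverse event collection without limiting it to one phase: the events "will be used to fully characterize the tolerability and toxicity of this combination therapy".

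**The concern.** Grade and relationship are the variables that define the rows of the planned tables. They are also the variables that decide whether a phase II event reaches the CRF. A table built for all patients from CRF data therefore has structurally empty phase II contributions in its grade 1-2 rows and in its unrelated rows of any grade. With a single denominator, a blank that means not collected reads as a patient without the event.

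What is at stake is the description of lower-grade and unrelated clinical toxicity. Such events can matter in practice: Table 2 holds ruxolitinib for grade 2 diarrhea that persists despite optimal treatment. Section 10.0 expects little gastrointestinal or other non-hematological toxicity, and a diluted row could seem to confirm that through the capture rule alone.

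**Working it through.** **Inputs.**
- Phase I patients, n1: up to 12 (Sections 6.0 and 8.1); 9 to 12 in the Phase I study paragraph of Section 8.1; a maximum of 18 evaluable in Section 13.0.
- Phase II patients, n2: up to 24 (Sections 6.0, 8.1 and 13.0). Phase I patients are not carried into phase II, so n1 and n2 add.
- Plan's own total: 12 + 24 = 36, which matches the stated maximum enrolment. The plan states no pooled adverse event rate.

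**Which rows are affected.**
- Grade 3 or above and related: in the CRF in both phases. Not affected.
- Serious, any attribution: reported through eSAE in both phases. Not affected if taken from those records.
- Laboratory grades and physical-exam findings: Table 3 gives the same schedule in both phases. Not affected. Laboratory grades include myelosuppression, the main toxicity expected with decitabine (Section 10.0).
- Non-serious, non-laboratory, and either grade 1-2 or unrelated: in the CRF in phase I only. Affected.

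**Size in an affected row.** Let p be the proportion of phase I patients with the event. Assume one pooled denominator, the CRF as the only source, and uncollected events counted as absent. Then

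pooled rate = (n1 × p + n2 × 0) / (n1 + n2) = p × n1/(n1 + n2).

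- Stated maxima: 12/36 = 0.333. An assumed phase I rate of 60% would appear as 20%, and an assumed 30% as 10%.
- Nine phase I patients: 9/33 = 0.273.
- Eighteen phase I patients with 24 in phase II: 18/42 = 0.429.
- Phase II stopping at 17 patients (the Table 9 average at 30% response and 20% toxicity), with 12 in phase I: 12/29 = 0.414.

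The factor is simply the phase I share of all patients. Its spread reflects the protocol's differing phase I maxima and possible early stopping, not uncertainty about the capture rule.

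**Rows not split by grade or relationship.** If q is the proportion of phase II patients with a recorded event of that type (grade 3 or above and related), the pooled rate is (n1 × p + n2 × q)/(n1 + n2). The dilution is then weaker than n1/(n1 + n2) whenever q is above zero.

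**If denominators follow capture.** With phase I patients alone as denominator for the affected rows, the factor is n1/n1 = 1 and the artefact disappears.

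**The case against.** The strongest reply is that the plan does not prescribe the dilution. It needs three things together: a pooled denominator, the CRF as sole source, and uncollected events scored as zero. Section 13.0 specifies none of these. It promises summaries for all patients without calling them pooled, and it names adverse event reports rather than the CRF as the source. A careful analyst would probably split by phase. That stands, and it makes the one-third figure conditional. It does not remove the conflict: the only stated presentation covers all patients by grade and relationship, and nothing tells the analyst to depart from it.

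A second reply is that the events are not lost, because source documents must hold every event with its attribution. That also stands. However, the supplied text contains no plan to retrieve lower-grade phase II events from source for the tables. Appendix E, to which adverse event recording is referred, is not in the text available and might alter what is captured.

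A reader might go further and infer that the trial's toxicity rates will be understated by two thirds. The documents do not support that. Phase I spans 10 to 50 mg BID in relapsed or refractory AML. Phase II uses one dose in AML arising from MPN, or MDS/MPN with more than 20% blasts. The phase I rate is therefore not the true all-patient rate, and the factor does not measure bias.

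Nor does the conflict undermine dose selection or stopping. The MTD rests on first-cycle DLTs in phase I, where capture is complete. Neither the Table 7 rule nor the primary response endpoint takes its input from these summaries. Narrower phase II capture is itself a legitimate choice; the point is only that the analysis text should acknowledge it.

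**Conclusion.** The point holds as a minor reporting correction. Two stated rules conflict, and the supplied text does not reconcile them. Followed literally, they give all-patient rows for non-serious, non-laboratory grade 1-2 or unrelated events in which up to 24 of 36 patients could contribute no recorded event. Under the three conditions set out above, such a row would show one third of the phase I rate at the stated maxima. The conclusion assumes that the CRF feeds the tables and that Appendix E does not widen phase II capture. No decision rule or primary result depends on it.

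**What to change.** Amend the safety paragraph of Section 13.0, Analysis method, as follows.

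- Present adverse event summaries separately for phase I and phase II, keeping cycle, grade and relationship.
- Limit combined-phase adverse event tables to data collected alike in both phases: related events of grade 3 or above, and SAEs. Take SAEs from the eSAE records, because unrelated phase II SAEs fall outside the CRF rule.
- Under every phase II and combined adverse event table, add a footnote stating the Section 14.1 capture rule.

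Tables by ruxolitinib dose, or a listing of dose at onset, are optional. Dose-level cells would hold only 3 to 6 patients, and doses may change after cycle 1.

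The cost is a few sentences and some extra table columns. It needs no new patients and no new data collection, because each patient's phase is already known.
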